## 9. Safety Analyses

All analyses of safety will be conducted using the Safety Set. All patients will be summarized according to the treatment they actually received, but the subgroup of topiramate patients who initially received topiramate and then switched to BOTOX will be summarized as follows:

- All safety assessments occurring prior to the date of the first dose of BOTOX will be summarized for the topiramate treatment arm.
- All safety assessments except AEs occurring on or after the date of the first dose of BOTOX will be summarized separately for the topiramate + BOTOX subgroup. For all AEs, the total number of patients (N) in each treatment arm will represent the number of patients that received that treatment. A patient may be counted in both treatment arms. The overall total will be the number of patients that received any treatment. The topiramate + BOTOX treatment arm will be a subset of the BOTOX treatment arm and will include patients that received both treatments. Denominators for percentages will be the total number of patients in each treatment arm or overall. Treatment-emergent AEs (TEAEs) include all AEs that start on or after the first dose of study medication up to the final visit, or are present prior to the first dose but increase in severity after the first dose of study medication up to the final visit. For patients who switch from topiramate to BOTOX, TEAEs starting on or after the date of the first BOTOX injection will be counted in the treatment arm that they are related to, as determined by a physician. If the TEAE is related to both treatments or if the relationship is unknown, it will be counted in both treatment arms but only once in the total. The topiramate + BOTOX subset will summarize all TEAEs that occurred after a patient has switched from topiramate to BOTOX.

Statistical hypothesis testing will not be performed on any safety results

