## 9.1. Adverse Events

An AE is defined as any untoward medical occurrence in a patient or clinical investigation subject administered a pharmaceutical product and that does not necessarily have a causal relationship with this treatment. An AE can therefore be any unfavorable or unintended sign (including an abnormal laboratory finding), symptom, or disease temporally associated with the use of a medicinal (investigational) product, whether or not related to the medicinal (investigational) product. In addition, during the screening period, AEs will be assessed regardless of the administration of a pharmaceutical product.

Adverse events will be assessed, documented, and recorded in the eCRF and will be classified by SOC and PT according to MedDRA version 16.0 or higher throughout the study (ie, after informed consent has been obtained). All AEs collected from the time of informed consent that are prior to study treatment will be defined as pretreatment AEs and will be presented in the listings.

A TEAE is defined as an AE that meets any of the following conditions:

- Begins on or after the first dose of study drug and before the final scheduled office visit at Week 36;
- Begins before the first dose of study drug and worsens in severity on or after the first dose of study drug and before the final scheduled office visit at Week 36;
- Is completely missing an onset date and the end date is on or after the first dose of study drug

If a patient receives BOTOX after receiving topiramate, the physician will be asked to determine if the AE is due to BOTOX or topiramate or unknown.

For the purpose of inclusion in TEAE tables, incomplete AE onset and end dates will be imputed as follows:

Missing onset dates (where “UK” and “UKN” indicate unknown or missing day and month respectively):

- UK-MMM-YYYY: If the month and year are different from the month and year of the first dose of study drug, assume the onset date is 01-MMM-YYYY. If the month and year are the same as the first dose of study drug month and year, and the end date (after any imputation) is on or after the first dose of study drug, then assume the onset date is the date of the first dose of study drug. If the month and year are the same as the first dose of study drug month and year and the end date (after any imputation) is prior to the first dose of study drug, then assume the end date for the onset date.

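### The TEAE windows in SAP 9 and 9.1 conflict for patients who switch to BOTOX, and both main adverse event columns mix two counting rules

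*SAP*

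**What the plan says.** **Window.** SAP 9 states: "Treatment-emergent AEs (TEAEs) include all AEs that start on or after the first dose of study medication up to the final visit". For patients who leave topiramate and receive BOTOX, SAP 3.1 and 3.4 put the final visit at Week 48. The definition in SAP 9.1 is different: "Begins on or after the first dose of study drug and before the final scheduled office visit at Week 36". Its clause on worsening events has the same Week 36 stop. Only the clause for a completely missing onset date has no upper limit. SAP 1 plans one lock after Week 36 and a final lock later, and says the plan serves both. SAP 9.1 does not limit its definition to the first.

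**Columns.** SAP 9 sets the denominators: "For all AEs, the total number of patients (N) in each treatment arm will represent the number of patients that received that treatment". Switchers therefore count in both arms, and "The topiramate + BOTOX treatment arm will be a subset of the BOTOX treatment arm". From the first injection on, switchers' events follow a causality rule: "TEAEs starting on or after the date of the first BOTOX injection will be counted in the treatment arm that they are related to", with a physician making that judgement. Events of shared or unknown cause are treated differently: "If the TEAE is related to both treatments or if the relationship is unknown, it will be counted in both treatment arms", though they enter the overall total once only. The subset itself has no causality filter: "The topiramate + BOTOX subset will summarize all TEAEs that occurred after a patient has switched from topiramate to BOTOX". SAP 9.1.1 applies this layout to the adverse event tables. It adds a by-cycle summary for patients treated with BOTOX and a by-patient listing.

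**Causality options.** In SAP 9.1, for patients given BOTOX after topiramate, "the physician will be asked to determine if the AE is due to BOTOX or topiramate or unknown". SAP 9.1.2 reports events as related or not related.

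**Use.** The second hypothesis in Protocol 2.2 rests on the between-group difference in adverse event rates and in discontinuations due to adverse events. SAP 9 rules out significance testing of safety results.

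**The concern.** The tolerability hypothesis has only descriptive rates behind it, so those rates need one clear definition. Two things stand in the way.

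First, two programmers following different sections of the same SAP would count different TEAEs for every switcher with an event in the last 12 weeks of follow-up. Under SAP 9.1 those patients still sit in the BOTOX denominator while part, or all, of their time on BOTOX cannot contribute to the numerator.

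Second, a reader comparing the BOTOX and topiramate columns is not comparing like with like. Each percentage joins events of any cause with events filtered by an attribution made in an open-label trial. The simple figure that the reader probably wants, the all-causality TEAE rate in patients randomised to BOTOX, is not among the tables described.

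**Working it through.** The SAP states no figure for the adverse event tables, so there is none to reproduce. The check is visit arithmetic and counting.

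**1. Window.** Inputs: a switcher's first BOTOX visit is Week 12, 24 or 36 (SAP 7.2), and the switcher's final visit is Week 48 (SAP 3.1, 3.4). For first injection at week w, post-switch time is 48 − w under SAP 9 and 36 − w under SAP 9.1.

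| First injection | SAP 9 (weeks) | SAP 9.1 (weeks) | Lost | Cycles inside SAP 9.1 |
|---|---|---|---|---|
| Week 12 | 48 − 12 = 36 | 36 − 12 = 24 | 12 of 36 (33%) | 2 of 3 |
| Week 24 | 48 − 24 = 24 | 36 − 24 = 12 | 12 of 24 (50%) | 1 of 2 |
| Week 36 | 48 − 36 = 12 | 36 − 36 = 0 | 12 of 12 (100%) | 0 of 1 |

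The target days in SAP Table 1 (85, 169, 253 and 337 for Weeks 12, 24, 36 and 48) agree: 337 − 85 = 252 days against 253 − 85 = 168; 168 against 84; 84 against 0. All three cycles of a patient randomised to BOTOX (Day 1, Weeks 12 and 24) lie inside both windows.

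A patient first injected at Week 36 has received BOTOX and is in that denominator. SAP 7.1 credits this patient with 84 + 1 = 85 days of BOTOX exposure. SAP 9.1 admits no TEAE with a known onset after that injection.

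**2. Counting rules.** Let N be the treated patients randomised to BOTOX, and A those with at least one TEAE. Let S be the switchers, k those with a post-injection TEAE counted to BOTOX, and m those with any TEAE in the topiramate + BOTOX subset.

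- BOTOX column: (A + k) / (N + S)
- Subset column: m / S
- Target: A / N

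The tables give A + k, N + S, m and S. N follows by subtraction; A does not, because k is not shown. Subtracting the subset count gives A + k − m, which equals A only if k = m. Since k lies between 0 and S, the tables place A between (A + k) − S and A + k, but do not fix it.

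The BOTOX column is a weighted average of A/N and k/S. It lies below the target if k/S < A/N and above it if k/S > A/N. Nothing in the documents says which applies.

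**3. Topiramate column.** Before the first BOTOX injection every TEAE counts. Afterwards a switcher's event counts only if related to topiramate, to both drugs, or unknown.

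**4. Post-switch event related to neither drug.**

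| Display | Is its place stated? |
|---|---|
| Topiramate + BOTOX subset | Yes, all post-switch TEAEs |
| Overall total | Yes, all treated patients |
| By-patient listing | Yes |
| BOTOX column | No |
| Topiramate column | No |

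SAP 9 covers one drug, both or unknown. SAP 9.1 offers BOTOX, topiramate or unknown. SAP 9.1.2 allows an event to be unrelated. The three lists do not match.

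**The case against.** The best case for the plan is that safety analysis by treatment received is prespecified (Protocol Summary and 7.1), and that physician attribution after a switch is a disclosed convention with an all-causality post-switch column beside it. That stands. As-treated analysis is not the fault here, and an extra column for patients randomised to BOTOX is an addition to the as-treated tables, not a replacement. It does not answer the window conflict.

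The two locks might be thought to explain the two windows. They do not: SAP 1 says the plan covers both analyses, and SAP 9.1 sets one definition without limiting it to the first. For patients who do not switch, the windows nearly agree, so the conflict is mainly about switchers.

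Several stronger readings are tempting and are not supported:

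- A reader might infer that the pooled column flatters BOTOX. The documents give no switch or event rates, so direction and size are both open.
- A reader might infer that subtracting the subset from the BOTOX column always understates the rate in patients randomised to BOTOX. That needs k ≤ m. SAP 9 starts the causality rule on the injection date itself, but describes the subset as events after the switch. If injection-day onsets fall outside the subset, k can exceed m. The SAP does not propose the subtraction in any case.
- A reader might infer that events related to neither drug vanish. They appear in the subset, the total and the listing; only their place in the two main columns is unstated.
- A reader might infer that only the BOTOX column is affected. The topiramate column is mixed too.
- A reader might infer that discontinuations due to adverse events are equally obscured. SAP 5 counts discontinuation reasons by treatment at the time, over randomised denominators, so they can be read there. SAP 9.1.5 uses treated denominators, which for BOTOX include switchers, and needs only a cross-reference.

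Finally, the table shells mentioned in SAP 4 are not in the documents and some protocol safety text is redacted, so the missing table is missing only from what can be seen.

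**Conclusion.** The point holds and should be fixed. SAP 9 and SAP 9.1 cannot both be followed for switchers. By nominal visits, SAP 9.1 removes 12 weeks of post-switch follow-up each time, which is one third, one half or all of it, while the patients stay in the BOTOX denominator. These are shares of observation time, not changes in an event rate, and actual visit dates will vary.

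Both main columns mix all-causality and attribution-filtered counts. No table visible in the documents gives the all-causality TEAE rate in patients randomised to BOTOX, and the planned columns bound it without determining it. The data are not lost, because the by-patient listings contain them. How far the published rates would be distorted, and in which direction, cannot be said. No efficacy analysis, test or sample size is affected; what is affected is the clarity of the adverse event rates behind the second hypothesis in Protocol 2.2.

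**What to change.** 1. Reconcile SAP 9 and 9.1 to one TEAE window that, in the final analysis, covers switchers' follow-up to their final visit. State the data cut for the Week 36 lock. Apply the same window to the by-cycle table in SAP 9.1.1.
2. Keep the as-treated tables. Add all-causality columns for (a) patients randomised to BOTOX, (b) topiramate before the first BOTOX injection, and (c) post-switch. Show for each the exposure that SAP 7.1 already plans to summarise, split to match. Use the same columns in SAP 9.1.5 and cross-refer that table to the disposition counts in SAP 5.
3. State which main column, if any, holds a post-switch event related to neither drug, and align the causality options in SAP 9, 9.1 and 9.1.2.

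The cost is SAP wording and a few table columns from data already collected. Two downsides should be stated in the SAP. Topiramate observation is shorter in patients who switch; showing exposure discloses this but does not correct it. BOTOX may start during the topiramate taper (Protocol 5.4.2.2, SAP 3.4), so topiramate events with onset in that overlap would fall in the post-switch column.

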2.2 Clinical Hypotheses

[figure not shown]
- BOTOX is more effective than topiramate as measured by the difference between treatment groups in a 50% responder rate (defined as the proportion of patients with a $\geq 50\%$ reduction from baseline in the number of headache days over a 28-day period).
- BOTOX has a superior tolerability profile than topiramate as measured by the difference between treatment groups in the rates of adverse events and discontinuations due to adverse events.
- BOTOX has an acceptable safety profile.

3. Study Design

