## 2. Objectives

The overall objective of this study is to compare the efficacy, safety, and tolerability of prophylactic treatment with BOTOX and topiramate in adults with CM.

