## 4. General Statistical Considerations

Continuous data will be summarized using descriptive statistics (ie, n, mean, standard deviation [SD], median, minimum, and maximum). Categorical data will be summarized using the patient count and percentage in each category. Confidence intervals (CIs) will be 95% and 2-sided, unless otherwise stated. Data will be displayed in all listings sorted by treatment group and patient number. P-values will be rounded to three decimal places. If a p-value is less than 0.001 it will be reported as “<0.001.” If a p-value is greater than 0.999 it will be reported as “>0.999.” Data will be displayed in all listings sorted by treatment group.

Patients will be identified in the listings by the patient identification number concatenated with the investigator number.

When count data are presented, the percentage will be suppressed when the count is zero in order to draw attention to the nonzero counts. A row denoted “Missing” will be included in count tabulations specified on the shells to account for dropouts and missing values. The denominator for all percentages will be the number of patients in that treatment group within the analysis set of interest, unless otherwise specified. Nonzero percentages will be rounded to one decimal place, except 100%, which will be displayed without any decimal places. Additional rounding rules are as follows:

- If the original value has 0 decimal places: mean, median, and CIs will have one decimal place and SD will have 2 decimal places
- If the original value has 1 decimal place: mean, median, and CIs will have 2 decimal places and SD will have 3 decimal places
- If the original value has 2 or more decimal places: mean, median, CIs, and SD will all have 3 decimal places

Minimum and maximum will always have the same decimal places as the original value, up to a maximum of 3 decimal places.

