## **5. Patient Disposition**

Patient disposition will be summarized for all enrolled patients and will include the number and percentage of patients for the following categories: patients randomized, patients treated (Safety Set), patients in the ITT Set, patients in the ssITT Set, patients in the PP Set, patients completed (study treatment and study), patients who discontinued study treatment (including patients who discontinued from topiramate and switched to BOTOX), and patients who discontinued from the study. Denominators for percentages will be the total number of patients randomized into each treatment arm, and overall.

The reasons for study treatment discontinuation and study discontinuation will also be summarized in this table. The reasons for treatment discontinuation may include any of the following: AE, death, lost to follow-up, withdrawal of consent, patient became pregnant, includes non-compliant with study treatment regimen, treatment was ineffective, treatment was no longer needed, existed study due to C-SSRS or other. The reasons for discontinuation will be counted in the treatment arm for which the patient was receiving treatment at the time of discontinuation. These treatment arms will include BOTOX, topiramate, and topiramate + BOTOX.

All patient disposition data will be presented in a listing

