### **9.1.1. Incidence of Adverse Events**

All AEs will be summarized for the Safety Set in the manner described in Section 9. Counts and percentage of patients with each type of AE will be provided. Denominators for percentages will be the total number of patients treated in each arm or overall. At each level of patient summarization, a patient is counted once if the patient reported one or more events.

An overview summary of the number and percentage of patients with any TEAE, serious TEAE, study drug-related TEAE, study drug-related serious TEAE, TEAE leading to treatment discontinuation, TEAE leading to study discontinuation, and AE leading to death will be provided by treatment arm.

Treatment-emergent AEs will also be summarized separately for each injection cycle for BOTOX treated patients.

The following summary tables will be repeated for any TEAE, serious TEAE, study drug-related TEAE, study drug-related serious TEAE, TEAE leading to treatment discontinuation, TEAE leading to study termination, and AE leading to death.

Summaries of the total number of TEAEs and the number and percentage of patients with at least one TEAE will be provided by treatment group. The number and percentage of patients and the number of events will also be presented by SOC and PT in descending order from the SOC with the highest total incidence (that is, summed across all treatment groups) to the SOC with the lowest total incidence. If the total incidence for any 2 or more SOCs is equal, the SOCs will be presented in alphabetical order. Within each SOC, the PTs will be presented in alphabetical order. At each level of patient summarization, a patient is counted once if the patient reported one or more events.

All AEs, will be presented in a by-patient listing.

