### **9.1.5. Adverse Events Leading to Treatment Discontinuation**

A summary of TEAEs with a study drug action taken of either “Drug Withdrawn” or “Switched to BOTOX” will be presented in a table. At each level of patient summarization, a patient is counted once if the patient reported one or more events. Counts and percentage of patients within each category will be provided. Denominators for percentages will be the total number of patients treated in each arm or overall.

Treatment-emergent AEs leading to treatment discontinuation will be categorized and presented by SOC and PT in a manner similar to that described in Section 9.1.1.

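### The protocol's superior-tolerability hypothesis gets no prespecified inferential answer: safety tests are barred, and no between-arm difference or interval is planned for either named measure

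*SAP*

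**What the plan says.** Protocol 2.2 lists three clinical hypotheses. The second is comparative and directional: "BOTOX has a superior tolerability profile than topiramate as measured by the difference between treatment groups in the rates of adverse events", to which it adds discontinuations due to AEs as a second measure. SAP 2 keeps a comparative aim, to "compare the efficacy, safety, and tolerability of prophylactic treatment with BOTOX and topiramate in adults with CM".

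SAP 9 states: "Statistical hypothesis testing will not be performed on any safety results". For AE incidence, SAP 9.1.1 says "Counts and percentage of patients with each type of AE will be provided". For AEs leading to treatment discontinuation, SAP 9.1.5 says "Counts and percentage of patients within each category will be provided". SAP 5 also tabulates AE discontinuations: "The reasons for discontinuation will be counted in the treatment arm for which the patient was receiving treatment at the time of discontinuation". It keeps BOTOX, topiramate and topiramate + BOTOX apart, with the numbers randomised as denominators.

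For the AE tables, SAP 9 says of switchers: "A patient may be counted in both treatment arms". It makes the topiramate + BOTOX group a subset of the BOTOX column, and it assigns events after the first BOTOX injection by the physician's judgement of relatedness. SAP 4 contains a general rule: "Confidence intervals (CIs) will be 95% and 2-sided, unless otherwise stated".

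**The concern.** Hypothesis 2 names a direction, a contrast and two measures, yet the visible plan never calculates the contrast. What results is percentages side by side with no measure of uncertainty. Any statement that BOTOX is better tolerated would then rest on reading two columns by eye, or on a difference and test chosen after the data are seen, in an open-label trial.

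Tolerability is not a side issue here. Protocol 1 motivates the study partly by topiramate's discontinuations for AEs, and the two earlier head-to-head studies it cites totalled 119 patients.

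**Working it through.** **1. Is a comparison planned anywhere visible?**

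| Place | What it gives on hypothesis 2 |
|---|---|
| SAP 9.1.1, AE incidence | Counts and percentages by treatment |
| SAP 9.1.5, AEs leading to treatment discontinuation | Counts and percentages by treatment |
| SAP 5, disposition | Counts and percentages of AE discontinuations, by treatment at the time |
| SAP 9.2 to 9.7 | Descriptive summaries and listings of other safety data |
| SAP 8 and 8.2, testing hierarchy | Primary and three secondary efficacy endpoints only |
| SAP 4, interval rule | Sets the format of intervals; no safety section asks for one |

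No difference, ratio, interval or time-to-event comparison appears for either measure. SAP 9 bars tests. It does not bar intervals, but none is planned.

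**2. Could a reader form the difference from the planned tables?**

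- *Discontinuations due to AEs: yes, crudely.* In SAP 5, take BOTOX AE discontinuations over patients randomised to BOTOX, minus topiramate AE discontinuations over patients randomised to topiramate. The topiramate + BOTOX group is separate and can be left out.
- *AE rates: no.* The SAP 9 columns are not the randomised arms. If s topiramate patients switch, they make up s/(200 + s) of the BOTOX column. For assumed s = 50, 100 or 150 this is 50/250 = 20%, 100/300 = 33% or 150/350 = 43%. Subtracting the subset does not undo this: the subset holds all post-switch events, while the BOTOX column takes only those judged related to BOTOX or to both, or of unknown relationship.

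**3. The plan's own sample size (efficacy only).** Inputs from Protocol 7.5: 28% v 44%, two-sided α = 0.05, power 90%, continuity-corrected chi-squared test.

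- Uncorrected: n = [1.96·√(2·0.36·0.64) + 1.2816·√(0.28·0.72 + 0.44·0.56)]² / 0.16² = 187.05, so 188.
- Corrected: (187.05/4)·[1 + √(1 + 4/(187.05·0.16))]² = 199.4, so 200 per arm.

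The stated 200 reproduces. The documents give no corresponding figure for tolerability.

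**4. What 200 per arm would give.** The documents state no expected AE rates for this trial, so all rates below are assumptions. Half-width = 1.96·√[p₁(1−p₁)/200 + p₂(1−p₂)/200]. Worked case, 25% v 5%: 1.96·√(0.0009375 + 0.0002375) = 0.067. Differences are shown as topiramate minus BOTOX; the sign reverses for BOTOX minus topiramate.

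| Measure | BOTOX v topiramate | Difference (points) | Half-width | 95% CI |
|---|---|---|---|---|
| AE discontinuation | 2% v 8% | 6 | 4.2 | 1.8 to 10.2 |
| AE discontinuation | 5% v 15% | 10 | 5.8 | 4.2 to 15.8 |
| AE discontinuation | 5% v 25% | 20 | 6.7 | 13.3 to 26.7 |
| AE discontinuation | 10% v 25% | 15 | 7.3 | 7.7 to 22.3 |
| Any AE | 40% v 50% | 10 | 9.7 | 0.3 to 19.7 |
| Any AE | 45% v 60% | 15 | 9.7 | 5.3 to 24.7 |
| Any AE | 50% v 80% | 30 | 8.9 | 21.1 to 38.9 |

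The half-width is largest at 50% v 50%: 1.96·√(2·0.25/200) = 9.8 points.

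**5. Power, if a test were wanted.** To apply the continuity correction, replace n by n − 2/d + 1/(n·d²), where d is the difference, and use the ordinary two-proportion power. For 2% v 8% this gives 200 − 33.3 + 1.4 = 168.1 and power 0.72. The others are 0.89 (5% v 15%), above 0.99 (5% v 25%), 0.48 (40% v 50%) and 0.83 (45% v 60%). The smallest difference detectable with 80% power is about 7 to 9 points at a BOTOX rate of 2% to 5%, and about 14.5 points at 40% to 50%.

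**The case against.** The strongest reply is that these are clinical hypotheses, not statistical ones. The third, on an acceptable safety profile, has no test or criterion either. The only formal null in the visible text is the primary efficacy null, and the sample size and hierarchy cover efficacy alone. Descriptive safety reporting is common practice. All of that stands, and a descriptive approach would be defensible if the SAP said so. It does not: the superiority hypothesis and the bar on tests stand together, unreconciled.

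Two stronger readings are tempting and should not be drawn.

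- *That the hypothesis cannot be answered at all.* Percentages are tabulated, and SAP 5 allows a crude randomised-arm difference in AE discontinuations. In addition, Protocol 6.2 and 7.3.3, SAP 3.2 and most of SAP 8.3 are not visible, so a planned interval there cannot be excluded. A planned safety test there would conflict with SAP 9.
- *That SAP 11 should have declared this as a deviation.* That section concerns departures from the protocol's specified analyses. If Protocol 7.3.3 planned descriptive safety reporting, there was nothing to declare.

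Power is also not assured: step 5 gives 0.48 for a 10-point difference in any AE at the assumed 40% v 50%.

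Finally, an interval measures sampling error only. It does not remove open-label bias. Nor does it remove the asymmetry in Protocol 8.8, where stopping topiramate leads to BOTOX and stopping BOTOX leads to study exit.

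**Conclusion.** The point holds in this form: hypothesis 2 receives no prespecified inferential answer in the visible plan. The two measures are affected differently. For AE discontinuations, a crude randomised contrast is recoverable but unplanned and without an interval. For AE rates, the planned columns do not give the randomised contrast at all.

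The sample size would support useful estimates, with a half-width of at most 9.8 points at 200 per arm and 4.2 to 7.3 points at the discontinuation rates assumed above. It would not guarantee a conclusive test. These figures rest on assumed event rates and on full arms of 200.

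This should be fixed, but it is not critical. The primary and secondary efficacy analyses are untouched, and what is at stake is how firmly a tolerability claim may be worded.

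**What to change.** In SAP 9, add an exception for the two measures in Protocol 2.2, and report BOTOX minus topiramate by randomised arm with a 95% CI.

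- **Discontinuation of randomised treatment due to an AE:** include all randomised and treated patients. A later stop of BOTOX after switching does not count as a second event.
- **Patients with at least one treatment-emergent AE (TEAE):** use a common window from Day 1 up to the Week 12 visit, the first at which a switcher can receive BOTOX. Add a pre-switch comparison over the full period, either exposure-adjusted or time to first event. Simple truncation at the switch is not enough: a patient who switches at Week 12 contributes about 12 weeks, against up to 36 on BOTOX. Fix the end of the full period as well, because SAP 9 runs TEAEs to the final visit while SAP 9.1 stops before Week 36.
- **Status of the hypothesis:** either define in advance how superiority would be tested (the order of the two measures, and whether both are needed), or state that hypothesis 2 is assessed by estimation only and that no formal superiority claim will be made. Placing the measures in the efficacy hierarchy is optional.
- **Limits:** state that the intervals do not correct for open-label reporting or for the different consequences of stopping in each arm.

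All other safety output can stay descriptive. The cost is SAP wording, two table rows, the supplementary full-period TEAE comparison, and a more cautious tolerability claim.
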